- [e] If the patient regains capacity but decides they do NOT wish to remain in the trial we will ask the patient to clarify one of the following: [i] they wish to be removed from the trial, decline any further tissue sampling or data collection and wish for all tissue samples already collected to be destroyed in accordance with local hospital policy. A withdrawal form will be completed. [ii] they do not consent to further tissue sampling but consent to the use of tissue samples that have already been collected. Agreement to tissue storage and use for the study will be documented on the consent form. All data collected up to the point of withdrawal will be retained.

- [f] Patients who die during the follow up period or do not regain mental capacity, will be included in the study based on the advice provided by the personal consultee and/or professional consultee. In cases where the subject dies before our attempt to obtain consent from the patient or the personal consultee, the patient will remain in the trial based on the consent obtained by the professional consultee and we will not attempt future telephone contact with relatives/personal consultee in order to minimise stress and anxiety associated with the unexpected and traumatic death of their relative / next of kin.
- [g] In general, the same procedures and principles will apply to the recruitment of paediatric patients with parents or legal guardians providing consent for children aged under 16 years who lack capacity. Paediatric patients who are Gillick competent will give consent for their own involvement. Wherever appropriate children will be involved in the discussion (with parents or legal guardians) regarding consent to use their samples and data. Discretion will be applied by the recruiting member of the research team regarding approaching a parent or legal guardian at all times, particularly during initial screening and recruitment in order to avoid causing undue stress and anxiety. Advice will be taken from the independent clinician in cases of uncertainty. Procedures for paediatric consent are detailed fully in appendix 2.

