SWiFT is a multi-centre, prehospital randomized control trial (RCT) to evaluate whether leukocyte-depleted Whole Blood (WB) stored at $2-6^{\circ}$ C is superior to standard of care (red cells and any form of plasma) in bleeding trauma patients. A total of 848 patients (424 in each arm) will be recruited over a 2-year period, with recruitment planned to start in June 2022. The trial is sponsored by NHS Blood and transplant (NHSBT) and funded jointly by NHSBT, nine air ambulance charities and UK Defence Medical Services. The primary objective of the trial is to determine whether WB transfusion (platelet rich) is better than standard care (blood component transfusion and/or lyosophilized plasma) in reducing 24 hr mortality or massive transfusion (defined as >10 units of any blood component) in patients with life-threatening haemorrhage.

International guidelines consider platelet transfusions integral to a massive haemorrhage protocol to treat trauma-induced coagulopathy although the mechanism by which platelets support coagulation and improve outcome are largely unknown. In severe

trauma patients, both thrombocytopenia and platelet dysfunction, as measured by decreased aggregation in response to agonists, have been shown to be directly associated with increased mortality. Even in the presence of a normal platelet count upon admission, dysfunction occurs in around half of critically injured patients and is an independent predictor of in-hospital mortality.

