To process and store samples for subsequent DNA typing and analysis. There appears to be a background race and genetic susceptibility to the effects of trauma. These alterations may well lie within the coagulation and inflammatory systems. Early identification of patients at risk may, in the future, allow therapy to be targeted depending on patients' racial background or even specific genetic make-up.

Primary Outcomes

Primary outcome is endogenous thrombin generation assessed via 10ml research blood sample collected within 60 minutes of arrival in the Emergency Department.

Secondary Outcomes

Secondary outcomes will include incidence of acute traumatic coagulopathy on arrival (defined by platelet count, prothrombin time, fibrinogen, fibrinolysis); admission blood lactate; admission clotting factor levels and markers of fibrinolytic activation/inhibition; quantitative analysis and phenotyping of microparticles; relative contributions of microparticle subtypes to thrombin generation.

STUDY POPULATION

Estimated number of patients to be enrolled: 386

Setting

Participating Major Trauma Centres (MTCs) receive trauma patients from the ten Air Ambulance Services that are participating the SWIFT trial. MTCs provide advanced multispecialty care for injured patients.

Study participants

Adult patients (>16 years) who been enrolled in the SWIFT trial and are admitted to the Emergency Department of a MTC will be considered for enrolment into the study. As the study is co-enrolling patients who have been recruited to SWIFT the ACIT SWIFT patients by definition will all have sustained life-threatening haemorrhage after major injury.

The study will, of necessity, include trauma patients who are unable to give consent for themselves and by definition are in an emergency clinical situation. Patients will be assessed for eligibility to enter study according to the criteria set out below. If patients are eligible for entry into the study, upon arrival in the Emergency Department, they will be enrolled automatically under a waiver of consent. See Ethics (Section 10) for further details.

The study may also include patients whose first language is not English. There is some evidence that patients from different racial groups have altered responses to injury, and excluding them would bias the study in favour of native English-speaking populations.

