Patients will be considered eligible for enrolment in ACIT SWIFT if they fulfil all of the inclusion criteria and none of the exclusion criteria detailed below.

Inclusion Criteria

Patients eligible for screening are adult (>16 years) trauma patients enrolled into the SWIFT prehospital randomized controlled trial and are transported to a Major Trauma Centre in England, Wales or North Ireland

Exclusion Criteria

Any patient who fulfils any of these criteria will not be considered for inclusion in the study:

- Transfers from other hospitals
- Burns >5% total body surface area
- >120 mins have lapsed since time of injury
- Deemed inappropriate for recruitment by an independent clinician (e.g. mass casualty event or futility)

STUDY DESIGN

ACIT SWIFT is a prospective cohort multi-centre observational sub-study of ACIT II that will co-enroll patients who have been recruited into SWiFT. Through a data sharing agreement between SWiFT and ACIT SWIFT it will enable capture of patient data from injury in the prehospital phase of care (when dosing for SWiFT occurs) with a ACIT SWIFT blood sample on admission to the emergency department. Data for SWiFT will be collected for the first 28 days or hospital discharge. Biomarkers from the blood sample will be compared between treatment arms in SWiFT and correlated with patient injury patterns, trauma-induced physiological disturbances and subsequent clinical course and outcome.

STUDY PROCEDURES

Informed Consent (same as primary ACIT study)

The standard operating procedure for obtaining consent is included in appendix 2.

Primary Outcomes

Primary outcome is endogenous thrombin generation assessed via 10ml research blood sample collected within 60 minutes of arrival in the Emergency Department.

Secondary Outcomes

Secondary outcomes will include incidence of acute traumatic coagulopathy on arrival (defined by platelet count, prothrombin time, fibrinogen, fibrinolysis); admission blood lactate; admission clotting factor levels and markers of fibrinolytic activation/inhibition; quantitative analysis and phenotyping of microparticles; relative contributions of microparticle subtypes to thrombin generation.

Screening and recruitment

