All SWiFT trial adult patients (aged 16 and over) who are admitted to the emergency department at an MTC via a trauma team activation will be screened for eligibility to ACIT-ED. As most SWiFT patients will be incapacitated at the time of screening it is anticipated that a waiver of consent will be used followed by initiation of the informed consent process at a time appropriate from the participant as described in Section 9.1.

Schedule of study interventions

Study Activity	Emergency	Discharge/
	Department	Day 28
History and Physical	SWIFT data	
Demographics	SWIFT data	
Injury characteristics	SWIFT data	
Physiological	SWIFT data	
observations		
Adverse events	ACIT-ED	ACIT-ED
Blood Sampling*	ACIT-ED	
Clinical outcomes		SWIFT

^{*}All patients have one blood sample taken on admission at the same as routine clinical blood tests

Study Intervention

Blood samples

SWiFT trial patients co-enrolled into ACIT SWIFT will have a blood sample drawn to measure activation of coagulation, fibrinolysis, endothelial injury and the immune system. The maximum sample volume for the single blood draw on admission will be 20ml. Severe trauma patients not enrolled into either SWiFT or ACIT would normally have blood samples drawn at minimum at 0, 12 and 24 hours and daily thereafter.

As most major trauma patients have an arterial or central line placed, particularly during the first 24hours when the ACIT SWIFT sample may be taken it will not be painful to the patient. When this is not the case, we will coordinate our blood draw with those of clinical need whenever possible, to minimise number of needle-sticks. We will not be able to use blood that has already been collected and placed into specimen tubes as our samples will require specific handling and processing.

There will be no serial blood sampling during the bleeding episode and at 24hr, 72hrs and Day 7 as research resource will not enable robust data collection 24/7 when SWiFT patients will be arriving at the MTC. The initial post-dosing sample after the SWiFT intervention has been delivered is the most important sample. As the patients will be randomized we can determine how whole blood transfusion improves hemostasis through comparison between trial arms.

Additional data collection

There will be no additional data collected for ACIT SWIFT(outside of the SWiFT trial which will be responsibility of the SWiFT team).

Patient questionnaires

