There will be no quality of life assessment collected as part of ACIT-ED. The UK Trauma & Audit Research Network (TARN) now routinely collects patient reported outcome measures on Day 28 and at 6 months which are available to MTCs locally and will be shared with the SWIFT trial team.

Procedure for collecting data

Data collection for this study will be limited to record of blood sample being taken and noted in the SWiFT trial to enable samples to be matched to the SWiFT study ID. It is the Investigator's responsibility to ensure the accuracy, completeness and timeliness of the record to ensure matching can take place.

Follow-up procedures

Follow up will be limited to SWiFT study procedures only.

Patient withdrawal

Each participant has the right to withdraw from the study at any time and for any reason without prejudice to his or her future medical care by the Investigator or at the institution.

Every reasonable effort will be made to maintain protocol compliance and to retain patient participation in the study consistent with the provisions of informed consent and good clinical practice. Additionally the PI may withdraw the participant. The following are potential reasons why a patient may be withdrawn from the study:

- Withdrawal of consent: the patient, the patient's authorised representative, independent physician, or designated individual who had provided initial consent to enter the study may withdraw consent at any time throughout the duration of the trial, without prejudice to future medical care and treatment.
- Retrospective exclusion: If a patient is deemed to not meet one or more of the inclusion/exclusion criteria in retrospect they will be withdrawn from the study.
- Major protocol deviation from the study design by the participant, observed or suspected by the investigator.
- Administrative: the sponsor or monitoring committees decide to terminate or discontinue the study.
- The participant's health would be jeopardised by continued participation and is withdrawn at the discretion of the investigator

Data collected up to the point of withdrawal will be retained. To safeguard the participants' rights, the minimum personally-identifiable information possible will be used.

Any samples obtained from withdrawn participants will be discarded in accordance with the local NHS Trust standard procedures. Samples sent to the central laboratory at the MTC will also be discarded.

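### ACIT SWIFT infers the effect of whole blood from randomisation alone, although the sampled patients are selected after randomisation and dosing

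*Protocol*

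**What the plan says.** All references are to the protocol. Appendix 4 describes ACIT SWIFT as an observational sub-study of patients already in the SWiFT randomised trial. SWiFT recruits and doses before hospital: "A total of 848 patients (424 in each arm) will be recruited over a 2-year period". Its primary objective concerns 24-hour mortality or massive transfusion.

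Entry to the sub-study comes later (Appendix 4, Study participants): "If patients are eligible for entry into the study, upon arrival in the Emergency Department, they will be enrolled automatically". The exclusions listed for sub-study entry include "Deemed inappropriate for recruitment by an independent clinician (e.g. mass casualty event or futility" and ">120 mins have lapsed since time of injury". The primary outcome is thrombin generation in one sample, due within 60 minutes of arrival.

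Under Patient withdrawal, Appendix 4 withdraws anyone found ineligible in retrospect, and then states: "Any samples obtained from withdrawn participants will be discarded in accordance with the local NHS Trust standard procedures". Yet its Informed Consent heading says the process is that of the primary study. There, section 11.1 [e] offers patients who decline to continue an option in which "they do not consent to further tissue sampling but consent to the use of tissue samples that have already been collected". Sections 9.7 and 11.1 [c] likewise let samples already taken be kept with agreement.

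On analysis, Appendix 4 (Study Design) says "Biomarkers from the blood sample will be compared between treatment arms in SWiFT". The Blood samples section draws the causal conclusion: "As the patients will be randomized we can determine how whole blood transfusion improves hemostasis through comparison between trial arms". The Statistical Considerations of Appendix 4 add 20% to the sample size, partly for uneven entry between the SWiFT arms.

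**The concern.** Randomisation makes the two full SWiFT arms comparable. It does not do so for a subset defined by events after treatment, some of which treatment may influence.

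The routes to look at are survival to the Emergency Department, the clinician's futility judgement, missed samples, retrospective withdrawal, and destruction of withdrawn patients' samples. Death is part of SWiFT's own primary endpoint, so a link between arm and survival to sampling cannot be dismissed. If more very sick patients survive to be sampled in one arm, that arm's mean thrombin generation falls for a reason unrelated to haemostatic effect.

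The discard rule can act in the same way. Under section 11.1 [f], patients who die stay in the study on consultee advice. Under [d] and [e], survivors who regain capacity are asked and may decline. With Appendix 4's rule their sample is then destroyed, so keeping the only primary measurement can depend on a later outcome that SWiFT's treatment aims to change. No later analysis can recover it.

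**Working it through.** **1. The plan's own figures.** Appendix 4 states 90% power, two-sided 5%, a 10% difference and 219 per arm. No standard deviation is given, so 219 can only be solved backwards:

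SD = 10 / [(1.960 + 1.282) × √(2/219)] = 32.3% of the mean.

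The inflation reproduces: 438 × 1.20 = 526.

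**2. How much of the randomised set is sampled.** The Summary and Study Population of Appendix 4 give 386; its Statistical Considerations give 526. That mismatch is a separate matter.

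- 386/848 = 45.5%
- 526/848 = 62.0%

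So 38% to 54% of the randomised patients would lie outside the comparison. This shows room for selection; it is not itself bias.

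**3. Survival route.** Assumptions, none from the document: 95% of the whole-blood arm survive to sampling; survival to sampling is 3 to 8 points higher than in the control arm; the extra survivors have thrombin velocity 30% to 70% below average.

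Fall in the whole-blood mean = (survival difference / 0.95) × relative deficit. The last two columns suppose a true benefit of 10%: observed benefit = 1.10 × (1 − fall) − 1, and power uses 193 per arm (386/2), with standard error 32.3 × √(2/193) = 3.29 points.

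| Survival gap | Deficit | Fall in mean | Observed benefit | Power |
|---|---|---|---|---|
| none | – | 0 | 10.0% | 86% |
| 3 points | 30% | 0.9% | 9.0% | 78% |
| 5 points | 50% | 2.6% | 7.1% | 58% |
| 8 points | 70% | 5.9% | 3.5% | 19% |

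The observed benefit stays positive throughout.

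**4. Second model, no true effect.** Assume thrombin generation is normal with SD 32.3%, and correlates at ρ with a normal latent tendency to be sampled. With r the proportion sampled in an arm, c the matching normal cut-off and φ the normal density:

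bias = ρ × SD × [φ(c)/r in whole blood − φ(c)/r in control].

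For r = 0.50 against 0.41, φ(c)/r is 0.798 and 0.948. At ρ = 0.5 the bias is 0.5 × 32.3 × (0.798 − 0.948) = −2.4 points.

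| Sampled, whole blood vs control | Size of spurious difference, ρ 0.3 to 0.7 | Two-sided type I error, 193 per arm |
|---|---|---|
| 45.5% vs 45.5% | 0 | 5% |
| 50% vs 41% | 1.5 to 3.4 points | about 7% to 18% |
| 95% vs 90% | 0.8 to 2.0 points | about 6% to 9% |

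The first row matters: equal sampling under the same mechanism in both arms gives no bias.

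**The case against.** The strongest reply is that the protocol nowhere says the comparison will be unadjusted. A statistical analysis plan may exist, and weighting, accounts of sampling by arm and sensitivity analyses commonly sit there. That stands, and their absence is not the finding. The finding is what the protocol does state: an unqualified inference from randomisation, and a discard rule that removes outcome data before any analysis plan could deal with them.

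A reader might infer from the low sampled fraction that the comparison is biased. The document does not support that. Its stated constraints, a cap of 10 centres and research staffing that does not allow round-the-clock work, need not differ by arm. Nor does it show how the 120-minute limit would depend on arm.

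A reader might also infer that selection could reverse a true benefit. On the assumed range, the worst case of 5.9% against 10% does not do so. The survival gap is itself uncertain: SWiFT's endpoint is a 24-hour composite, whereas the sample is due within an hour of arrival, so the composite does not establish a gap of 3 to 8 points by then.

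Finally, the discard conflict is partly an inconsistency in its own right. It biases the comparison only if withdrawal differs by arm and relates to thrombin generation, and neither is shown. It still matters, because following the Appendix 4 wording destroys the primary measurement irrecoverably.

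**Conclusion.** The point holds in a limited form. The causal sentence in the Blood samples section claims more than the design can deliver. The analysed set is formed after dosing, so the comparison can be biased where selection differs by arm and relates to thrombin generation. Enlarging the sample for uneven entry improves precision and leaves bias untouched.

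That the sampled set is formed after randomisation is certain from the text. The size and direction of any bias are not: every input in steps 3 and 4 apart from the back-solved SD and the planned numbers is an assumption. On those assumptions the shift is about 1% to 6% against the 10% target. That can attenuate or hide an effect, and can raise the type I error when there is none. The conflict over withdrawn patients' samples needs no assumption.

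**What to change.** 1. **Qualify the inference.** In Appendix 4, Blood samples, say that the comparison is by randomised arm among patients who reached the Emergency Department and were sampled, and that it is open to selection after randomisation.
2. **Account for everyone.** Report by arm, out of all SWiFT patients randomised, how many were sampled, died before sampling, were excluded, were missed or were withdrawn.
3. **Add sensitivity analyses.** Keep the comparison of sampled patients as the main one, since unsampled patients have no assay and a direct comparison of all 848 is impossible. Add inverse-probability-of-sampling weights built on SWiFT covariates measured before randomisation, and a worst-rank analysis for deaths before sampling. Appendix 4 (Data management) says the data-sharing agreement is still to be drawn up; it must cover baseline data on unsampled SWiFT patients, or the weights cannot be built.
4. **Reconcile the discard rule.** Bring Appendix 4, Patient withdrawal, into line with sections 9.7 and 11.1 [c] and [e], since Appendix 4 itself says consent follows the primary study.

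A prospective change to eligibility is not proposed: the sub-study's proposed end date was June 2024, before this protocol version of July 2024.

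The cost is wording, a flow table by arm, two added analyses and the scope of the data agreement. The weights rest on measured covariates only and widen the interval slightly.

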In our lab we have performed ex vivo pilot work to evaluate the effect of whole blood and platelet concentrates on coagulopathic blood sampled from bleeding trauma patients in ACIT soon after arrival in the Emergency Department. Platelet concentrates and whole blood appear to primarily prevent dilutional effects and further deterioration in platelet dysfunction, clot strength and clot formation times typically observed during current MHP transfusion. This preliminary analysis using rotational elastometry (ROTEM) demonstrates a signal for improved thrombin generation profiles of coagulopathic blood mixed with whole blood compared to red cell and plasma transfusion. Data from this work have been used for the sample size calculations for the primary outcome (thrombin generation) and allows for 25% dropouts and

STUDY POPULATION

Estimated number of patients to be enrolled: 386

STUDY AIMS and OBJECTIVES

AIM 1: Characterize the therapeutic mechanism and efficacy of whole blood transfusion in trauma major haemorrhage

Determine the key derangements and describe trauma specific phenotypes in coagulation, fibrinolytic, platelet and endothelial cell function following major injury; determine the response to whole blood therapy and anti-fibrinolytic medication.

Hypothesis ACIT-ED

Whole Blood transfusion is better than standard care (component transfusion and/or lyosophilized plasma) in correcting acute traumatic coagulopathy and supporting haemostasis during major trauma haemorrhage.

AIM 2: Coagulopathy and Massive

Transfusion

Characterize the key derangements and describe trauma specific phenotypes in coagulation, fibrinolytic, platelet and endothelial cell function following major injury; determine the response to blood component therapy and anti-fibrinolytic medication; and further characterize the subsequent hypercoagulable state.

AIM 3: Genomic, proteomic and lipidomic analysis

To process and store samples for subsequent proteomic, transcriptomic, lipidomic and genomic techniques to identify new loci for investigation, targeting drug discovery and identification of genetic susceptibility to poor outcome following trauma and transfusion.

AIM 4: Trauma DNA Bank

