The study withdrawal form will be completed for these patients and a reason for withdrawal captured where possible. All participants withdrawn from the study will be managed in accordance with the hospital's standard procedures.

End of Study Definition

Patients are followed up when in hospital in accordance with the SWiFT protocol which is daily until day 28, death or discharge (whichever occurs sooner). If patients remain in hospital beyond day 28, their electronic records will be periodically reviewed remotely until discharge to enable collection of any outstanding endpoint data.

STATISTICAL CONSIDERATIONS

Ex vivo work at the Centre for Trauma Sciences in which patients with ATC had blood samples spiked with either whole blood, or red cells & plasma, has demonstrated a 12% increase in the maximum velocity of thrombin generation in those samples spiked with whole blood. ACIT-ED will use 90% power to detect an increase in maximum velocity of thrombin generation of 10% at 5% significance level and a two tailed test. The required sample size to meet specified power requirements is 438 patients in total (219 in each arm). We have increased this by 20% to allow for drop outs, unbalanced recruitment to ACIT-ED across arms of the SWiFT trial and sampling errors leading to a total of 526 participants.

ETHICS

This study as a sub study of ACIT II will be carried out in accordance with the ethical Principals in the Research Governance Framework for Health and Social Care, Second Edition, 2005 and its subsequent amendments as applicable and applicable legal and regulatory requirements. The ACIT II study has been reviewed and approved by the Research Ethics Committee: London – City and East (07/Q0603/29).

11 Safety Considerations

All parts of the study will be carried out to avoid patient risk and minimize discomfort at all times. At no time will patient care be compromised or delayed for the purposes of the study.

We will record all adverse events associated with the study and review them as they occur, and collectively at monthly intervals. Participation in research may involve some degree of loss of privacy. However, this risk will be minimized by our data protection methods and we are not performing any tests that might subsequently result in significant personal, financial or social risk to the research subjects. We will make every effort to ensure that our data is

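### Appendix 4 gives incompatible sizes for ACIT SWIFT: 386 to be enrolled, against 438 evaluable (526 with allowance) for the stated 90% power

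*Protocol*

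**What the plan says.** All the places are in the protocol's Appendix 4, which describes one sub-study under two names, ACIT SWIFT and ACIT-ED.

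- **Statistical Considerations.** The ex vivo work "has demonstrated a 12% increase in the maximum velocity of thrombin generation in those samples spiked with whole blood". The design target is smaller: "ACIT-ED will use 90% power to detect an increase in maximum velocity of thrombin generation of 10"%. The test is specified as two-sided at the 5% level. The result is given as "The required sample size to meet specified power requirements is 438 patients in total (219 in each arm"). This is then increased by 20% to cover dropouts, imbalance in recruitment between the SWiFT arms, and "sampling errors leading to a total of 526 participants".
- **Summary table.** The number of participants is 386.
- **Study Population, which appears twice** (once before the aims and once after the outcomes). Both say "Estimated number of patients to be enrolled: 386".
- **Rationale, last paragraph.** The ex vivo data were used to size the study on thrombin generation, and the calculation "allows for 25% dropouts". The sentence breaks off after the next word.

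No text reconciles 386 with 438 or 526, or marks any of them as superseded.

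**The concern.** A loss allowance can only raise a required number. No allowance applied to 438 can give 386, so the two figures cannot come from the same calculation, and a reader cannot tell which one governs recruitment.

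This matters because Section 10 of the main protocol says a power calculation does not apply to ACIT II as a whole. The whole blood versus component comparison in Appendix 4 is therefore the only comparison in the protocol with a stated power. If recruitment stops at 386 while the 90% statement stays in place, the chance of missing a true 10% difference is at least 14%, and about 22% to 25% after the losses mentioned in the appendix, instead of the stated 10%. The total also sets how many of SWiFT's 848 patients must be co-enrolled: 386/848 = 46%, or 526/848 = 62%.

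**Working it through.** **Inputs, all from Appendix 4.** Two-sided 5% test, 90% power, 10% increase, 219 per arm (438 in total), 20% increase, 526 total, 25% dropouts, 386 enrolled. Equal arms and losses equal between arms are assumed. The normal approximation for two means is used.

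**Step 1. Reproduce the plan's own total.** 438 × 1.20 = 525.6, which rounds up to 526. The figure reproduces.

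**Step 2. Effect size implied by 438.** With z(0.975) = 1.960 and z(0.90) = 1.282, the sum is 3.242. From n per arm = 2 × (3.242/d)², d = 3.242/√(219/2) = 3.242/10.464 = 0.310. A 10% difference then corresponds to an SD of about 32% of the control mean. This is back-solved, not stated in the protocol.

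**Step 3. Power for 10% at 386.** At any evaluable total N, power = Φ(3.242 × √(N/438) − 1.960). The SD cancels, so only the ratio of N to 438 matters, provided the variability behind 438 applies.

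**Step 4. Difference detectable with 90% power.** This is 10% × √(438/N).

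| 386 enrolled | Evaluable N | 3.242 × √(N/438) | Power for 10% | Detectable at 90% power |
|---|---|---|---|---|
| no loss | 386 | 3.043 | 86.1% | 10.7% |
| 20% lost | 308.8 | 2.722 | 77.7% | 11.9% |
| 25% lost | 289.5 | 2.635 | 75.0% | 12.3% |

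**Step 5. Sensitivity.**
- A t-test in place of the normal approximation gives 86.0%, 77.6% and 74.9%.
- If 386 is read as already multiplied by 1.20, the evaluable number is 386/1.20 = 321.7 and power is 79.3%. If multiplied by 1.25, it is 308.8 and power is 77.7%.
- None of these readings reaches 90%.

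**Step 6. Size of the gap.** 438 − 386 = 52 (12% below the evaluable requirement). 526 − 386 = 140 (27% below the inflated total).

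**The case against.** The strongest reply is that the protocol never says 386 is the operative target. If 526 is, the statistical section is consistent with itself, the 90% statement stands, and 386 is only a figure left uncorrected in three places. This reply stands, and it makes the shortfall conditional.

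A second reply is that 386 may come from another calculation, with a different SD or target effect. With the back-solved SD, 90% power for a 12% effect needs 219 × (10/12)² = 152.1, so 153 per arm or 306 in total, and 306 × 1.25 = 382.5, close to 386. That is conjecture: the statistical section sets the target at 10%. If it were true, two incompatible calculations would sit in one appendix, which is the same problem. It does mean that the 75% to 78% figures hold only if the variability behind 438 applies to 386.

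The conflict between the two allowances is weaker than the conflict between the totals. The 25% sentence is cut off, possibly by the reading of the PDF, and the 20% is a composite increase, not a dropout rate.

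On timing, the sub-study's proposed end was June 2024, before protocol version 8.0 of 16 July 2024. The correction may therefore bear more on reporting than on recruitment, though the protocol does not say whether recruitment has closed.

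**Conclusion.** The contradiction is real and has to be resolved: 386 cannot stand beside 438 and 526. If 386 is operative, power for the stated 10% increase is about 86% at best and about 75% to 78% after 25% or 20% loss. The difference detectable with 90% power rises to about 11.9% to 12.3%, roughly the full ex vivo effect, so the margin gained by designing for 10% is gone. These figures assume equal arms and the variability implied by 438.

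A reader might infer three stronger things that the protocol does not support:

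- **That the sub-study is underpowered outright.** This follows only if 386 is the target, and the protocol does not say so.
- **That 526 is itself miscalculated, because multiplying by 1.20 does not fully offset a 20% loss.** The text says the number was increased by 20% for several reasons together, and 526 is exactly that. Even with 20% lost from 526 (about 421 evaluable), power is 88.8%.
- **That the absence of an SD is a separate error.** That detail may lie in an analysis plan not shown here, and the comparison of 386 with 438 does not need it.

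**What to change.** State one enrolment total, one target effect and one loss allowance, and make them agree in the Appendix 4 summary table, the rationale, both study population sections and Statistical Considerations.

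- **If 526 is operative:** correct 386 in its three places and align the 25% in the rationale with the 20% increase.
- **If 386 is operative:** replace the 90%/438/526 statement with the basis of 386 and the power it delivers. If the variability behind 438 still applies, that is about 75% to 78% for a 10% increase after the losses mentioned in the appendix.

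The cost is wording in Appendix 4. With 386, the stated power becomes less favourable but no further patients are needed. With 526, the documents would openly commit to co-enrolling about 62% of SWiFT in place of 46%. If recruitment has already closed, the correction should be made before the results are reported.
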